10.2. SECONDARY EFFICACY VARIABLE(S)

Change from baseline in the Western Ontario & McMaster Osteoarthritis (WOMAC) Index Total Score at each week

The change from baseline in the WOMAC Index total score will be analyzed using an MMRM with treatment (placebo vs CR845) and treatment-by-week interaction as fixed effects, baseline value and OA joint (hip vs knee) as covariates, and patient as a random effect. The primary comparison between groups will be based on estimates and contrasts for the weeks 4, 6, and 8 means. The comparison at week 8 will be viewed as secondary. A 95% CI will be constructed for the weeks 4, 6 and 8 mean differences between CR845 and placebo based on the MMRM.

The MMRM model (based on observed data) will be implemented using SAS PROC MIXED. REML will be used. An appropriate covariance matrix will be used to model the within patient errors. An appropriate covariance matrix will be used to model the within patient errors until there are no convergence issues in the following order: 1) unstructured, 2) Toeplitz, 3) autoregressive [1], 4) compound symmetry, 5) variance components. The Kenward-Roger approximation will be used to estimate the denominator degrees of freedom and adjust standard errors.

Change from baseline in the WOMAC Pain Intensity, Stiffness and Function Sub-scale Scores at each week

The change from baseline in the WOMAC sub-scales for pain intensity, stiffness and function will be analyzed using an MMRM model similar to the one presented above for the WOMAC index total score.

Treatment Pain Response: Proportion of patients with a X0% improvement from baseline in the weekly mean pain intensity at week 8

The proportion of patients with a response to treatment that is $\geq 30\%$ will be analyzed using logistic regression, including treatment, baseline weekly pain score, and OA joint as independent variables. Site will be included as a random effect. Additionally, the proportions will be compared using a Cochran-Mantel-Haenzel test stratified by OA joint (hip or knee) and

dichotomized baseline weekly pain score (<6.7 , ≥ 6.7). These analyses will be repeated for patients who have a response to treatment $\geq 50\%$.

The cumulative proportion of patients that achieve at least 10%, 20%, 30%, 40%, 50%, 60%, 70%, 80%, 90% and 100% response to treatment will be summarized and plotted for each treatment.

Patient Global Impression of Change (PGIC) at Week 8 or End of Treatment visit

The PGIC will be summarized as both a categorical and continuous variable (including 95% CI for the mean). The proportion of patients with PGIC scores of “Very Much Improved” and “Much Improved” will also be summarized and compared between treatments using a logistic regression with treatment as a main effect and OA joint as a covariate. Additionally, this proportion will be compared using a Cochran-Mantel-Haenzel test stratified by OA joint (hip or knee) and dichotomized baseline pain score (<6.7 , ≥ 6.7).

Supplemental Analgesic Medication Used: Average daily number of acetaminophen tablets used over the study and during the Maintenance Treatment Period

The average daily number of acetaminophen tablets used during the study and during the Maintenance Treatment Period will be compared between treatments using a Wilcoxon Rank Sum Test stratified by Primary OA Joint (Hip or Knee) and dichotomized baseline pain score (<6.7 , ≥ 6.7) (van Elteren test⁴). The categorized groupings will also be summarized.

Proportion of patients withdrawing from treatment due to lack of analgesic efficacy

The proportion of patients withdrawing from treatment due to lack of analgesic efficacy will be analyzed using logistic regression, including treatment, baseline pain score, and OA joint as independent variables. Additionally, the proportions will be compared using a Cochran-Mantel-Haenzel test stratified by OA joint (hip or knee) and dichotomized baseline pain score (<6.7 , ≥ 6.7).

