STATISTICAL METHODS (continued)

For the primary efficacy analysis, the treatment of missing data will be addressed using pattern mixture model methodology. Within each treatment, 4 data patterns will be defined as follows:

- Pattern 1: will include patients who completed treatment on study drug.
- Pattern 2: will include patients who discontinue treatment early due to adverse events. Missing data for these patients will be assumed to be similar to their pain score prior to the start of treatment.
- Pattern 3: will include patients who discontinue treatment early due to lack of efficacy. Missing data for these patients will be assumed to be similar to their pain score prior to the start of treatment.
- Pattern 4: will include patients who discontinue treatment early due to reasons other than adverse event or lack of efficacy. Missing data for these patients will be assumed to be similar to the scores for patients that are still in the study and randomized to the same treatment group.

The pattern mixture model methodology will be implemented using SAS procedures MI and MIANALYZE.

Sensitivity analyses will be conducted to assess the impact of the treatment of missing data on the study results. The analysis of the secondary efficacy variables is presented in Section 11 of the protocol.

Safety and Tolerability:

All safety data (AEs, clinical laboratory tests, and vital signs) will be listed by patient and summarized by group and time point as appropriate. Adverse events will be coded to preferred term (PT) and system organ class (SOC) using the Medical Dictionary for Regulatory Activities (MedDRA).

Interim Assessment

An IA is planned when approximately 50% of the planned 405 patients have been randomized and have either completed the 8-week treatment period or have discontinued from treatment early. The IA will include a re-estimation of the final target sample size based on conditional power.

SAMPLE SIZE DETERMINATION

With 270 patients assigned to active treatment and 135 patients assigned to placebo (2:1 randomization), a total sample size of 405 patients will be sufficient to detect an effect size of 0.343 with > 90% power and a type 1 error rate of 5%.

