If a patient's mean weekly pain score during the last week of the Maintenance Treatment Period is greater than the baseline score (i.e., the patient has an increase in pain compared to baseline), his/her response to treatment will be assigned a value of 0. Patients who discontinue study drug early will be considered non-responders to treatment and will be assigned a pain response of 0.

A graph of percentage of patients who have a treatment pain response $\geq 10\%$, $\geq 20\%$, $\geq 30\%$, $\geq 40\%$, $\geq 50\%$, $\geq 60\%$, $\geq 70\%$, $\geq 80\%$, $\geq 90\%$, and $\geq 100\%$ will be presented. In addition, the proportion of patients with a response to treatment that is $\geq 30\%$ will be analyzed using logistic regression, including treatment, baseline pain score, and OA joint as independent variables. The cutoff of 30% was chosen as it has been shown to represent a clinically important improvement in pain. This analysis will be repeated for patients who have a response to treatment $\geq 50\%$.

Patient Global Impression of Change (PGIC)

The PGIC score collected at Week 8, or at the End of Treatment visit (for patients who discontinue treatment early) ranges from 1 (Very Much Improved) to 7 (Very Much Worse). The count and proportion of patients in each response category will be displayed for each treatment group. In addition, summary statistics (n, mean, standard error, median, minimum, and maximum) and 95% CI for the mean treatment response will be tabulated.

The proportion of patients with PGIC scores of "Very Much Improved" and "Much Improved" will be analyzed using logistic regression with treatment as a main effect, and OA joint as a covariate.

Supplemental Analgesic Medication Used

Acetaminophen is the only allowable rescue medication for pain beginning from Day -5 until the end of the Maintenance Treatment Period. Acetaminophen will be provided as 325-mg tablets with a maximum allowable dose of 8 tablets per day (given every 4 to 6 hours as needed).

However, the use of acetaminophen is not allowed for the 12 hours prior to a scheduled office visit until after the efficacy assessments have been completed, in order to minimize the confounding effects of rescue medication on these measures.

Protocol CR845-CLIN2002-PO

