3. STUDY OBJECTIVES

The primary objective of this study is to characterize the analgesic efficacy of orally administered CR845 in patients with OA of the hip or knee.

There are 4 secondary objectives:

- To compare the treatment effect on patient function, pain and stiffness between CR845- and placebo-treated patients as measured by the Western Ontario and McMaster Osteoarthritis Index (WOMAC).
- To compare the treatment effect on Patient Global Impression of Change between CR845- and placebo-treated patients.
- To compare the use of analgesic rescue medications between CR845- and placebo-treated patients.

- To characterize the safety and tolerability of titration-to-effect administration of oral CR845.

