
The PGIC score collected at Week 8, or at the End of Treatment visit (for patients who discontinue treatment early) ranges from 1 (Very Much Improved) to 7 (Very Much Worse).

Supplemental Analgesic Medication Used

The average daily number of acetaminophen tablets used during the study will be calculated using data recorded in the patient diary as the sum of the total number of tablets used divided by the length of exposure (in days). A similar algorithm will be used to derive the average daily number of acetaminophen tablets used during each week (baseline will be study day -5 to study day -1), the Titration-to-Effect Period, the Maintenance Treatment Period, Study Day 1 to 56 Period and the End of Treatment week

Due to the nature of the data, the average daily number of analgesic rescue use (in this case acetaminophen) tend to have a large portion of zeroes (contributed by subjects not taking any supplemental pain medication) followed by continuous distribution of non-zero values. Therefore, the supplemental pain medication for OA will be grouped categorically into the following classes: (1) no supplemental acetaminophen tablets, (2) 0 to \leq 0.5 tablets, (3) $>$ 0.5 to \leq 1.0 tablets, (4) $>$ 1.0 to \leq 2.0 tablets, and (5) $>$ 2.0 tablets.

Withdrawal Due to Lack of Analgesic Efficacy

This will be obtained from the treatment completion form of the eCRF.

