8. GENERAL STATISTICAL CONSIDERATIONS

This SAP contains a detailed description of the analytical variables and the statistical methods/procedures that will be presented in support of this clinical study (CLIN2002-PO). Any modification to the proposed analyses will be documented in the integrated statistical/clinical report. Additionally, any exploratory analyses not described in the Statistical Analysis Plan will be documented in the integrated statistical/clinical report.

The overall objectives of this study will be achieved through descriptive and/or inferential analyses involving the efficacy and safety variables collected in this study. All variables specified in the protocol will be reported in listing format. All such variables (other than those used purely for screening purposes) and resulting change from baseline values will be summarized using descriptive statistics for each treatment group. Selected change from baseline values will be compared between the treatment groups statistically. Within this general framework, attention is called to variables that will be used to evaluate the primary hypothesis, pre-specified secondary hypotheses, and additional hypotheses of special interest.

The primary population for efficacy analysis will be the FAP population. Sensitivity analyses based on the PP population will be conducted for the primary efficacy variable if greater than or equal to 20% of FAP patients are excluded from the PP population. The primary population for safety analysis will be the safety population (see Section 7.0 for definitions)

All hypothesis tests comparing CR845 and placebo will be two-sided and conducted at the 5% significance level, unless otherwise specified.

All summary tables will be presented by treatment group (if applicable) and over all patients in the analysis population being summarized. Continuous variables will be summarized using the following descriptive statistics: n, mean, SD, median, minimum, and maximum. Categorical variables will be summarized using counts and percentages. Unless specified otherwise, percentages presented will be calculated using all patients in the analysis population being summarized (with randomized or received treatment as/if appropriate) as the denominator.

SAS® Version 9.2 or later will be used to produce all statistical tables, listings and figures to be contained in Section 14 of the integrated statistical/clinical report.

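### SAP 10.2 tests the 7-point PGIC between arms only as a top-two-category proportion, and its logistic model omits the baseline pain score used in the SAP's other two secondary logistic models

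*SAP*

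**What the plan says.** One of the four secondary objectives is "To compare the treatment effect on Patient Global Impression of Change between CR845- and placebo-treated patients" (SAP 3; same aim in Protocol 5.2). PGIC is the only measure that serves it. The scale has seven ordered categories and is collected once, at Day 57 or early termination (Protocol 9.2.1.3).

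SAP 10.2 summarizes the full scale as categories and as a mean with a 95% CI, without a between-arm test. What is tested is the proportion in the two best categories, in two ways:

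- It is "compared between treatments using a logistic regression with treatment as a main effect and OA joint as a covariate".
- A CMH test on the same proportion is stratified by OA joint and baseline pain (below 6.7, or 6.7 and above).

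Protocol 11.8.1 has the same logistic model: the top-two proportion "will be analyzed using logistic regression with treatment as a main effect, and OA joint as a covariate". It has no CMH test.

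Elsewhere in SAP 10.2, withdrawal for lack of efficacy is "analyzed using logistic regression, including treatment, baseline pain score, and OA joint as independent variables", and the pain-response model also includes the baseline weekly pain score. Average daily rescue tablets are compared by a van Elteren test with the same joint-by-baseline-pain strata as the PGIC CMH test.

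**The concern.** Two features stand out.

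1. Seven ordered categories are reduced to two for every between-arm test. A move from No Change to Minimally Improved, or fewer patients worsening, would appear in the descriptive table but contribute nothing to either test.
2. The PGIC logistic model leaves out a covariate that is already collected and that the SAP's other two secondary logistic models use. No reason is given.

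At stake is the sensitivity of the only comparison serving this objective. SAP 8.5 says that results on endpoints other than the primary may inform hypotheses and the choice of endpoints for later studies, so a missed PGIC effect could influence that choice.

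**Working it through.** **Inputs from the documents.** 270 CR845 and 135 placebo patients; effect size 0.343 with power above 90% for the primary endpoint (Protocol synopsis); two-sided 5% tests (SAP 8). No power, distribution or effect is given for PGIC.

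**Assumptions, not in the documents.** Placebo PGIC distribution 7/22/30/30/7/3/1% from best to worst, so 29% in the top two; no missing PGIC; no covariates in steps 2 to 4. Step 3 varies the placebo distribution.

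**Step 1: the plan's own figure.** Power = Φ(d/√(1/270 + 1/135) − 1.96) = Φ(0.343/0.1054 − 1.96) = Φ(1.294) = 0.902. The stated figure for the primary endpoint reproduces.

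**Step 2: effect across the whole scale.** With a common odds ratio (OR), each cumulative placebo proportion p becomes OR·p/(1 − p + OR·p) on active.

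- Two-category power = Φ((|p1 − p0| − 1.96·s0)/s1), with s0 and s1 the standard errors of the difference under the null and the alternative.
- Rank-test power = Φ((|θ − 0.5| − 1.96·σ0)/σ1), with θ the probability that an active patient scores better than a placebo patient, ties counted half, and σ0, σ1 the tie-corrected null and alternative standard errors.

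Example, OR 1.6:

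- Two categories: p1 = 0.464/1.174 = 0.395; s0 = 0.0506; s1 = 0.0491; (0.1052 − 0.0992)/0.0491 = 0.12; power 55%.
- Full scale: θ = 0.573; σ0 = 0.0294; σ1 = 0.0291; (0.0728 − 0.0577)/0.0291 = 0.52; power 70%.

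| OR | Top two, active | Rank vs two-category, formula | Rank vs two-category, rerun | Gap in rerun |
|---|---|---|---|---|
| 1.4 | 36.4% | 43% vs 31% | 43% vs 31% | 12 points |
| 1.6 | 39.5% | 70% vs 55% | 70% vs 56% | 14 points |
| 1.8 | 42.4% | 87% vs 75% | 88% vs 75% | 13 points |

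**Step 3: other placebo distributions.** Assume instead a shift of 0.343 on an underlying normal scale. That number is the design effect for pain, borrowed here only for scale. The rank test has 86% to 87% power. The two-category test has 50%, 65%, 71% and 73% when 10%, 20%, 30% and 40% of placebo patients are in the top two. At a shift of 0.25 the figures are 60% to 61% against 28%, 39%, 44% and 47%. The gap depends strongly on the assumed placebo distribution, but all these cases still assume that the whole scale moves.

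**Step 4: other effect patterns.** Same placebo distribution as step 2.

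- *Effect at the responder threshold.* Twelve points move from Minimally Improved to Much Improved, giving 41% vs 29%. Two categories: (0.12 − 0.0997)/0.0492 = 0.41, power 66%. Rank: θ = 0.531, (0.0312 − 0.0577)/0.0289 = −0.92, power 18%. Sending some of the 12 points to Very Much Improved raises the rank figure (23% in one simulated case) but does not change the order.
- *Some active patients worsen.* OR 1.6, with 5% of active patients moved from categories 3–4 to 6–7: rank 43%, two-category 55%. With 3% moved, both are about 55%.

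**Step 5: the missing covariate.** 4,000 simulated trials per row; further assumptions: 30% placebo responders, shift 0.343, hip share 25%.

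| Correlation of baseline pain with PGIC | Logistic as planned | Logistic plus baseline pain | CMH as planned |
|---|---|---|---|
| 0 | 72.1% | 72.0% | 72.0% |
| 0.2 | 70.5% | 71.2% | 70.8% |
| 0.4 | 70.8% | 75.5% | 73.6% |

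At correlation 0.4 the planned CMH test recovers (73.6 − 70.8)/(75.5 − 70.8) = 2.8/4.7, about 60% of the difference.

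**The case against.** The strongest reply is that the top-two proportion is a responder definition, prespecified identically in protocol and SAP and in keeping with the 30% and 50% cut-offs used for pain response. Such a definition deliberately does not count Minimally Improved as success. This stands, and is a reason to keep the comparison.

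A reader might infer that the dichotomy simply gives away power on this objective. The documents do not support that. Step 4 shows the ranking reversing, and neither document says which pattern to expect. Some worsening on active is conceivable: early terminators complete PGIC and are analysed, and in the Phase 2a study 4 patients in the 5-mg group of 20 stopped because of dizziness (Protocol 4.2.1).

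A reader might also infer that PGIC is tested with no account of baseline pain, or that the SAP breaks its own covariate rule. Neither holds. The CMH test stratifies by baseline pain. SAP 8.1 requires OA joint throughout but a baseline value only for change-from-baseline and repeated-measures models; PGIC is neither. At protocol level the contrast is weaker still, because the withdrawal model there names no covariates.

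Finally, the consequence is limited. The trial is powered for the primary endpoint only, SAP 8.5 makes that the key result, and no decision rule depends on a PGIC p-value. What remains is an unexplained difference between similar models in one section, and a comparison that ignores most of an ordered scale when a suitable rank test is already specified for rescue medication.

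**Conclusion.** The concern holds as a modest matter of efficiency and consistency, not as an error. The full PGIC scale has no between-arm test, and the PGIC logistic model lacks the baseline pain score found in the SAP's other two secondary logistic models.

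- **Covariate:** roughly 0 to 5 power points for an assumed correlation of 0 to 0.4, in the logistic model only.
- **Dichotomy:** about 12 to 14 points (up to 15 by formula) in favour of a full-scale test, if a common odds ratio of 1.4 to 1.8 acts on the assumed placebo distribution. The advantage is larger if few placebo patients are responders, and reversed if the effect sits at the responder threshold or about 5% of active patients worsen.

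The further conclusion that a full-scale test should replace the top-two comparison does not follow. Each test is stronger under a different pattern, so a full-scale test belongs beside the responder analysis.

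**What to change.** In SAP 10.2, before unblinding:

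1. Add the baseline weekly pain score to the PGIC logistic model, alongside treatment and OA joint.
2. Keep the top-two comparison and state that it is the prespecified PGIC responder analysis.
3. Add one supportive comparison of all seven categories: the van Elteren test stratified by OA joint and baseline pain (<6.7, ≥6.7), as already specified for rescue medication. Label it supportive, so that it cannot be promoted over the responder result afterwards.

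The cost is a few lines of SAP text and one procedure call, with no new data and no change for patients. The downsides are one more unadjusted secondary p-value and a rank-based result that is harder to interpret than a difference in proportions.

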5.2 Secondary Objectives

- To compare the treatment effect on patient function, pain and stiffness between CR845- and placebo-treated patients as measured by the Western Ontario and McMaster Osteoarthritis Index (WOMAC).
- To compare the treatment effect on Patient Global Impression of Change between CR845- and placebo-treated patients.
- To compare the use of analgesic rescue medications between CR845- and placebo-treated patients.
- To characterize the safety and tolerability of titration-to-effect administration of oral CR845.

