9.1.1 Screening and Washout

Each patient must be screened within 14 days before randomization in the study. The following procedures will be performed at Screening:

- 1. Obtain written informed consent.
- 2. Review inclusion/exclusion criteria.
- 3. Collect demographic information.
- 4. Record medical history (including duration of OA symptoms), and prior and current therapies (e.g., prescription and non-prescription medications).
- 5. Identify the index joint for the study.
- 6. Review how to complete assessment of pain intensity for the identified joint using the NRS.
- 7. Obtain a pain intensity score for the index joint using the NRS.
- 8. Review with the patient how to complete the WOMAC and Patient Global Impression of Change (PGIC).
- 9. Perform a physical examination including weight and height.
- 10. Collect vital signs (including body temperature).
- 11. Perform a 12-lead ECG.
- 12. Obtain blood and urine samples for drug screening, serum pregnancy (women of childbearing potential only), and clinical laboratory evaluations (including serum sodium measurement where sodium level must be ≤ 143 mmol/L). If sodium level is > 143 mmol/L,

then the patient can be retested in approximately 1 hour after being given a glass of water to drink.

13. If patient is eligible:

- a. Instruct patient to discontinue current pain medications 5 days prior to the Baseline Visit (Washout is Days -5 to -1). Instruct patients how to assess and record in the Patient Diary their pain intensity score and number of rescue medication tablets taken each evening for the 7 days prior to the Baseline Visit.
- b. Dispense rescue medication (acetaminophen).
- c. On Day -7, contact the patient to remind him or her about the washout week and the collection of daily pain scores.
- d. Schedule Visit 2 (Baseline; Day 1).

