Patients will record their pain intensity score (all days), the number of rescue medication tablets taken for target or other pain (Day -5 onwards) and AM/PM dosing of study drug (Day 1 onwards) in a patient diary.

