8.1. ADJUSTMENTS FOR COVARIATES

All statistical analyses of efficacy variables comparing CR845 versus placebo will be adjusted by the location of the primary OA joint (hip vs knee) unless otherwise specified.

Statistical models without repeated measures which compare the change from baseline endpoints will additionally be adjusted for the value observed at baseline prior to first dose of treatment and effect of the study center.

Mixed Models with Repeated Measures (MMRM) comparing results which are included across all time-points will additionally be adjusted for the baseline value, week, treatment by week interaction and the effect of the patient.

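### The rescue-acetaminophen test in SAP 10.2 is valid but leaves out each patient's own baseline rescue use, which the SAP already derives, so it may give up efficiency

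*SAP*

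**What the plan says.** Protocol 5.2 lists as a secondary objective: "To compare the use of analgesic rescue medications between CR845- and placebo-treated patients".

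Protocol 9.1.1 has patients record in the diary their pain score and the "number of rescue medication tablets taken each evening for the 7 days prior to the Baseline Visit". SAP 4.1 starts the rescue record at Day -5. Either way, intake before treatment is available.

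SAP 5.1.2 derives average daily tablets for each week and period, and includes a pre-treatment value: "baseline will be study day -5 to study day -1".

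SAP 10.2 then compares the whole-study and Maintenance Treatment Period averages by a "Wilcoxon Rank Sum Test stratified by Primary OA Joint (Hip or Knee) and dichotomized baseline pain score", the pain score being cut at 6.7. Baseline rescue use is neither a stratum nor a covariate.

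The general rule in SAP 8.1 does not bring it in: "Statistical models without repeated measures which compare the change from baseline endpoints will additionally be adjusted for the value observed at baseline". The only other own-baseline rule there is for repeated-measures models. Average tablets per day is not a change from baseline, and it is not analysed with repeated measures.

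**The concern.** Some patients may take acetaminophen readily and others hardly at all, whatever their treatment. If such differences persist from baseline into the treatment period, they remain as noise in a test that ignores baseline intake. Stratifying by pain above or below 6.7 removes only the part that baseline pain explains.

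The omission also departs from the SAP's practice elsewhere. The NRS and WOMAC models adjust for their own baseline, and the pain-response regression includes baseline pain. PGIC and withdrawal for lack of efficacy have no baseline of their own. Rescue use is the one secondary endpoint whose own baseline is derived but left out of its comparison.

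At stake is power on a secondary comparison, not the validity of its p-value.

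**Working it through.** **Inputs from the documents.** 270 CR845 and 135 placebo patients; two-sided 5% level; a standardised effect of 0.343 with more than 90% power for the primary endpoint (Protocol synopsis). No power is stated for rescue use. SAP 5.1.2 expects many zeros but gives no proportion.

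**Assumed, because the documents are silent.** The correlation ρ between baseline and on-treatment rescue use, the share of zeros, the size of the rescue effect, and the correlation of baseline pain with rescue use.

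**Step 1: the plan's own figure.** SE of a standardised difference = √(1/135 + 1/270) = 0.1054. Power = Φ(0.343/0.1054 − 1.96) = 90.2% (90.1% with the noncentral t). The stated figure of more than 90% reproduces.

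**Step 2: simple formula.** Adjusting for a baseline with correlation ρ multiplies the residual SD by √(1 − ρ²). Take a rescue effect that has 80% power unadjusted: (1.96 + 0.842) × 0.1054 = 0.295 SD. Adjusted power = Φ(0.295/(0.1054·√(1 − ρ²)) − 1.96), and the equivalent unadjusted trial size is 405/(1 − ρ²).

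| ρ | Variance removed | Adjusted power | Equivalent unadjusted N |
|---|---|---|---|
| 0.2 | 4% | 81.6% | 422 |
| 0.3 | 9% | 83.6% | 445 |
| 0.5 | 25% | 89.9% | 540 |
| 0.7 | 49% | 97.5% | 794 |

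This ignores the zeros and the pain stratum, so it serves only as a guide.

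**Step 3: simulation of the two rank tests.** Each simulation has 405 patients at 2:1 and many zeros, and compares the van Elteren test with a stratified rank ANCOVA on baseline rescue use.

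| Simulation | Correlation | van Elteren | Adjusted | Gain (points) |
|---|---|---|---|---|
| A | Spearman 0.36 | 75% | 81% | 6 |
| A | Spearman 0.54 | 74% | 88% | 14 |
| A | Spearman 0.70 | 78% | 96% | 18 |
| B | latent 0.2 (Spearman 0.18) | 82.9% | 83.5% | 0.6 |
| B | latent 0.3 (Spearman 0.26) | 82.7% | 83.6% | 0.9 |
| B | latent 0.5 (Spearman 0.45) | 81.8% | 87.7% | 5.9 |
| B | latent 0.7 (Spearman 0.64) | 81.6% | 95.0% | 13.4 |

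A: effect 0.3 SD on the latent scale, tablets limited to 0–8 per day, 1,500 runs per cell. B: effect 0.32 SD on the latent scale, about 30% zeros, pain correlated 0.3 with rescue use, 3,000 runs per cell. The Monte Carlo SE of one rate in B is about √(0.83 × 0.17/3,000) = 0.7 point, so its gains at 0.2 and 0.3 are close to nil. Type I error was 4.3–5.4% in A and 4.7–5.1% in B, over both tests.

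**Step 4: how much the pain stratum already recovers.** Simulation C (effect 0.3 SD, about 30% zeros on placebo, 2,000 runs per cell) varied the correlation between pain and rescue use.

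- Spearman 0.36, pain unrelated to rescue use: 76.0% against 81.5%, a gain of 5.5 points, close to A.
- Spearman 0.36, pain correlated 0.3 or 0.5 with rescue use: the gain falls to 3.7 or 1.5 points.
- Spearman 0.18–0.27: about 0 to 1.5 points.
- Spearman 0.55: still about 9 to 11 points.

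**The case against.** The planned test is not an error. Randomisation protects its type I error, and that error rate already allows for chance imbalance in baseline use. Any imbalance would also be visible, because SAP 8 and 10 call for descriptive summaries of every efficacy variable. This stands: the issue is efficiency, not bias.

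The correlation may be low. Days -5 to -1 are the washout, when NSAIDs and opioids are stopped, so intake may reflect their withdrawal rather than habit. Five days are set against up to 56. The 12-hour ban before scheduled visits may touch one of those days, and rescue is allowed for any pain. This also stands, and it is why the gain could be near zero.

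The endpoint is modest. It is one of six listed secondary endpoints. SAP 8.5 treats results other than the primary as material for future hypotheses, and Protocol 11.8.1 planned only descriptive and categorical summaries of rescue use, so the SAP test already goes further. This limits the priority of the change but is no reason to leave out a baseline that is already derived.

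A reader might infer that baseline rescue use is the best predictor of later use, or that this test is the main check on whether acetaminophen masks a pain difference. The documents support neither: they give no data on prediction and assign the test no such role.

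**Conclusion.** The point holds as a low-cost gain in efficiency. The planned van Elteren test is valid but does not use a baseline that the trial records and the SAP derives. Adding it gains about 0 to 1 point of power at a correlation of 0.2 to 0.3, about 6 to 14 points near 0.5 and about 13 to 18 points near 0.7, and less where baseline pain already predicts rescue use. These figures rest on the assumed correlations, share of zeros and effect sizes above.

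A reader might go further and conclude that the trial certainly loses material power here, or that the comparison is biased. Neither follows. The correlation is unknown and the washout baseline may limit it, and both tests held their level in simulation. What can be said is that the adjusted test was not less powerful at any setting reported in A or B and was clearly better at moderate and high correlation.

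**What to change.** Before unblinding, amend SAP 10.2 as follows:

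- Make the comparison a stratified rank ANCOVA. Keep the strata for OA joint and baseline pain (<6.7, ≥6.7), and add as covariate the rank of average daily acetaminophen tablets on Days -5 to -1.
- Apply it to both the whole-study and the Maintenance Treatment Period averages.
- Average whatever baseline diary days are available. Give patients with no baseline rescue diary the overall mean baseline rank, so that none are dropped. State that this fills a covariate only; the SAP 8.2 rule against imputing the endpoint is unchanged.
- Keep the van Elteren test as a supportive analysis.

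The cost is a few lines of text and code. No new data, visits or patients are needed.
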